1.1 Trial summary

Title	A phase I-II trial of a combination of Nintedanib, an oral VEGF inhibitor, in combination with induction chemotherapy for patients with refractory or first relapse acute myeloid leukemia
Indication	Treatment of patients with relapsed/refractory AML as defined by the WHO
Design	Phase I- randomized II study
Sponsor	YALE UNIVERSITY
Contact	[name] PhD [contact] [contact] Email: [contact]
Products	Nintedanib/ placebo, idarubicin, cytarabine
Summary of Rationale	Nintedanib is an oral VEGF inhibitor with a good tolerance profile. There is evidence of a potential clinical impact of VEGF inhibition in AML and some in vitro evidence of activity of Nintedanib against AML blasts. Given that outcome of relapse/refractory AML patient is poor and that no standard option is available for this group of patients, we anticipate that a combination of nintedanib+ induction chemotherapy may be an effective strategy for this group of patients.
Treatment plan	
Phase I: Patients who meet eligibility criteria and sign informed consent will receive the following during an inpatient hospital stay; Idarubicin 12mg/m²/d IV Push over 10-15 minutes days 1 to 3, cytarabine 0.667g/m²/d (24 hr.) IV infusion day 1 to 3 and Nintedanib 200mg BID PO day 8-28. There will be no drug administered on days 4-7. Length of inpatient hospital stay is based on local site SOP.
 
Phase II: Patients who meet eligibility criteria and sign informed consent will receive the following during an inpatient hospital stay; Idarubicin 12mg/m²/d IV Push over 10-15 minutes days 1 to 3, cytarabine 0.667g/m²/d (24 hr.) IV infusion day 1 to 3 and Nintedanib 200mg BID PO on day 8-28 OR placebo. There will be no drug administered on days 4-7. Length of inpatient hospital stay is based on local site SOP.
 
For both Phase I and II, a maximum of 2 induction and 2 consolidation cycles may be given, cycles are 28 days.
 
During Phase II, all Patients failing to achieve response based on IWG 2003 AML response criteria after cycle 1 will be unblinded, and all those who had been receiving placebo will be offered Nintedanib+ chemotherapy (cross over) for cycle 2. Patients in the Nintedanib arm can be given a second cycle of Nintedanib.
 
Nintedanib maintenance treatment will be given to responding pts not eligible for Hematopoietic stem cell transplantation (HCT) for up to two years or until disease progression. Patients eligible for HSCT will be taken off study prior to HSCT.

Primary objective	
Phase I: To determine the safety and tolerability of a combination of Nintedanib + induction chemotherapy.
 
Phase II: To determine the efficacy (rate of CR/CRp/CRi) of Nintedanib+ induction chemotherapy vs. Placebo+ induction chemotherapy

Secondary objectives	
 • Overall response rate according to IWG AML 2003 criteria • Toxicity profile and safety of the combination • Percentage of patients bridging to transplantation • Overall survival, leukemia free survival including analysis with censoring at HSCT • Rates of haematological improvement according to IWG MDS 2006 criteria • Correlative studies
Inclusion criteria	
Patient must meet all of the following inclusion criteria to be eligible for the study
 
1/ Patient aged 18y or older
 
2/ Diagnosis of AML according to WHO 2008 criteria. Therapy related to AML may be included if off treatment for their prior malignancy for more than 2 years and in complete remission. AML arising after documented Myeloproliferative Disorder (MPD) is excluded.
 
3/ Patient must meet one of the following 2 criteria:
 
 • Patient refractory (not responsive) to one or two standard induction regimens • Patients with a first untreated relapse within 2 years of documentation of complete remission. Patients relapsing after allogeneic stem cell transplantation are eligible if more than 6 months after transplantation and without signs of active Graft vs Host Disease (GVHD). 
4/ Patient may have been pre treated with intermediate to high dose cytarabine (More than 1000mg/m²/d over 5d) if the day of the last infusion was at least 90 days before inclusion in the study.
 
5/ ECOG performance status of 2 or less
 
6/ Patient is willing to participate to the study, has the ability to adhere to the study visit schedule and other protocol procedures, and has the ability to understand and signs an informed consent form.
 
7/ Women of childbearing potential must agree to use effective contraception without interruption through the study and for 3 months after the end of treatment;
 
8/ Men must agree to not conceive during the treatment and to use effective contraception during the treatment period (including periods of dose reduction or temporary suspension) and for 3 months after the of treatment if their partner is of childbearing potential.

Exclusion criteria	
Any of the following criteria excludes the patient from participating to the study.
 
1/ Patient with documented acute promyelocytic leukemia and/or PML-RAR transcript.
 
2/ Patient relapsing more than 2 years after initial remission.
 
3/ Use of any active treatment for relapse/refractory AML including but not restricted to chemotherapy, targeted agents, hypomethylating agents or investigational drugs. Use of hydroxyurea up to 6g per day for cytoreduction is allowed for a maximum of 30 days prior treatment.
 
4/ Patients with clinical evidence of active Central Nervous System (CNS) disease at enrollment
 
5/ LVEF below 45% or lifetime exposure to anthracyclines over 350mg/m² of daunorubicin equivalent
 
6/ Liver function tests: AST ALT above 2.5 ULN, total bilirubin above 2.5 ULN in the absence of Hemolysis or diagnosis of Gilbert's syndrome
 
7/ Serum creatinine above 2.0mg/dl
 
8/ Any sign of active uncontrolled disease including but not restricted to cardiac disease, infections, hepatitis. Any severe chronic disease potentially interfering with the protocol including HIV infection, active hepatitis B or C. It includes major injuries and/or surgery within the past 4 weeks prior to start of study treatment with incomplete wound healing and/or planned surgery during the on-treatment study period.
 
9/ Documented platelet refractoriness
 
10/ Patient has a history of GI surgical procedures, non-surgical procedures or conditions that might interfere with absorption or swallowing of the study drugs.
 
11/ Women who are or pregnant, or who are currently breastfeeding
 
12/ Prior treatment with nintedanib or any other VEGFR inhibitor. With the exception for treatment of prior malignancies with a VEGFR inhibitor.
 
13/ Known hypersensitivity to nintedanib, any other trial drug, or their excipients
 
14/ Persistence of any clinically relevant (CTCAE grade 2 or above) non -haematological toxicities from previous AML therapy
 
15/ Active alcohol or drug abuse
 
16/ Any other condition that, according to the investigator, may forbid the administration of the idarubicin+cytarabine regimen
 
17/ Therapeutic anticoagulation with INR modifying drug or use of antiplatelet therapy (with the exception of low dose aspirin<325mg/d)
 
18/ Any malignancies requiring active treatment within the past year other than basal cell skin cancer or carcinoma in situ of the cervix. Patients actively treated with hormone therapy for prostate cancer or breast cancer are eligible.

---------------------------	---

Planned of duration of the study	2 years of accrual, 2 years of follow-up
Number of patients	22 to 60 patients according to the evaluation (see below statistical methods)
Safety Analysis	An independent safety review committee (SRC) assembled by the PI and comprised of one Investigator from both Yale, and Vanderbilt, two external AML experts and a statistician will meet, when required by the sponsor of the trial, and at least once after the inclusion of the first 6 patients, to analyze tolerance and adverse events and decide on any action to be taken.
Statistical methods	Phase I will use a classical 6+6 design. A n-1 dose level is schedule if DLTs are observed at initial dose level Phase II will use an adaptive randomized design. A minimum of 8 patients will be included in each arm and continuous reassessment method will be used after each patient to evaluate futility or success of each specific arm of treatment.
Patient follow-up	Phase I patients will be followed up to 60 days after the last study drug administration in order to determine if any DLTs are attributable to Nintedanib. Patients will then be followed every 3 months +/- 7 days for 24 months or until the patient begins receiving subsequent anti-cancer therapy or death, whichever comes first. Phase II patients will be followed every 3 months +/- 7 days 24 months or until the patient begins receiving subsequent anti-cancer therapy or death, whichever comes first.

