1.3 Objectives

1.3.1 *Primary objective*

Phase I: To determine the safety and tolerability of Nintedanib in combination with intensive AML chemotherapy; Idarubicin and cytarabine after 1 cycle of treatment

Randomized Phase II: To determine the complete remission rate (CR+ CRp) of chemotherapy ; Idarubicin and cytarabine + nintedanib compared to chemotherapy Idarubicin and cytarabine +placebo after 1 cycle of treatment

1.3.2 *Secondary Objectives*

To determine overall response rate of nintedanib+ chemotherapy as compared to placebo + chemotherapy

To determine the overall survival and leukemia free survival of patients treated with nintedanib+chemotherapy as compared to placebo+chemotherapy.

To determine the percentage of patients bridging to allogeneic transplantation as well as time to transplantation after nintedanib+chemotherapy as compared to placebo+chemotherapy

To determine hematological response rate of the nintedanib+ chemotherapy as compared to placebo + chemotherapy

Phase II: To determine the safety and tolerability of nintedanib+chemotherapy as compared to placebo+chemotherapy

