1.4.2 Secondary endpoints

Overall response rate will be defined according to IWG 2003 criteria⁴⁶ and includes: CR, CRp, CRI, PR, and marrow leukemia free state (MLFS). Rates of hematological improvements (as defined by IWG 2006 Myelodysplastic syndromes criteria⁴⁷) will also be recorded.

Overall Survival will be defined from time of treatment initiation to the time of last follow-up or death. Survival with censoring patients at the time of transplantation will also be evaluated.

Leukemia free survival will be defined from time of documentation of complete remission (CR+CRp+CRI) to the time of last follow-up, relapse, or death of any cause. Survival with censoring patients at the time of transplantation will also be evaluated.

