In phase II, patients failing to achieve response based on IWG 2003 AML response criteria after cycle 1 will be unblinded, and all those who had been receiving placebo will be offered a cycle of Nintedanib+ chemotherapy (cross over). Patients in the Nintedanib arm may receive a second induction cycle of Nintedanib. Based on clinical judgement, patients can receive up to 2 cycles of consolidation after induction cycle (s) are complete.

Patients are eligible for allogeneic transplantation as soon as remission is achieved and a donor is identified. All transplant procedures occur off study. For responding patients not eligible for transplantation, maintenance therapy with Nintedanib/Placebo will be provided until documented progression.

Patients should NOT start Cycle 1 day 1 on a Thursday or Friday in order to facilitate sample collection, processing and shipment to Sponsor to avoid weekend deliveries.

[figure not shown]

Figure 2. Global treatment strategy of the Phase II portion of the study

NIN/PLA: Nintedanib/ Placebo, CR: complete response, CRp: CR with incomplete counts recovery. Patients can receive up to 2 induction and 2 consolidation cycles.

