1.18 Follow-up

1.18.1 Phase I:

Phase I patients will be followed up to 60 days after the last study drug administration in order to determine if any DLTs are attributable to Nintedanib. When counts have not recovered by day 60 and there is no morphological evidence of leukemia it is considered a Nintedanib associated hematologic DLT. Sixty days is the maximum length of time to wait for someone to recover before they are removed from the study.

Patients will then be followed every 3 months +/- 7 days for 24 months or until the patient begins receiving subsequent anti-cancer therapy or death, whichever comes first. The following information will be collected; first subsequent anti-cancer therapy (if applicable), documentation of last disease progression/relapse, and date of death. Patients or their caregivers will be contacted by phone.

1.18.2 Phase II:

Phase II patients will be followed every 3 months +/- 7 days for 24 months or until the patient begins receiving subsequent anti-cancer therapy or death, whichever comes first. The following information will be collected; Information regarding the first subsequent anti-cancer therapy (if applicable), documentation/date of last disease progression/relapse, and date of death. Patients or their caregivers will be contacted by phone.

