f: Idarubicin may be dose reduced, replace, or omitted according to total dose of anthracycline received by the patient

g: Twice weekly for an Induction Cycle

h: Weekly; Cycle 2 ONLY

i: Three times weekly

j: Prior to Cycle 2: Any time after Cycle 1 day 14 up to the start of cycle 2; 3d Echocardiogram or biplane Simpson method are acceptable methods for obtaining LVEF

k: Performed in patients with complete clearance of blasts in the blood

l: Every other week

m: differential for CBC will only be done as per hospital standard of care (Required at screening, response evaluation and end of treatment visit)

o: AEs and Concomitant Medications will be assessed on an ongoing basis

p: prior to the start if each new treatment cycle

Maintenance Cycle, End of Treatment & Follow Up

	Maintenance Therapy																				Every 3 months (+/- 7 Days) up to 2 years		
	Monthly (+/- 3 days) for the first 12 months then every 3 months (+/- 7 Days) until disease progression or up to 2 years																						
Month	1	2	3	4	5	6	7	8	9	10	11	12	14	15	16	18	20	21	22	24	End of Treatment	Follow-Up	
Nintedanib ^a	X	X	X	X	X	X	X	X	X	X	X	X	X	X	X	X	X	X	X	X			
Concomitant Medications ⁱ																							
Physical Exam ^b	X	X	X	X	X	X	X	X	X	X	X	X		X		X		X		X	x		
ECOG PS	X	X	X	X	X	X	X	X	X	X	X	X		X		X		X		X	x		
AEs ⁱ																							
CBC with differential ^f	X	X	X	X	X	X	X	X	X	X	X	X	X	X	X								
Serum chemistry ^c	X	X	X	X	X	X		X		X	X		X	X	X		X	x		x			
Pregnancy Testing ^j	X	X	X	X	X	X	X	X	X	X	X	X	X	X	X	X	X	X	X	x ^j	x ^j		
Coagulation Profile ^d	X		X		X																		
EKG, Cardiac Echo ^g																					x		
Bone Marrow Evaluation ^e																					x		
Correlative Studies (Blood & Bone Marrow)																					x		
Hematology, CBC & hemoglobin																					x		
Subsequent anti-cancer therapy, documentation/date of last disease progression/relapse, date of death																						x	

a: Continuous/daily

b: Complete physical exam and vitals including weight, blood pressure, pulse, temperature, respiratory frequency

c: Serum chemistry: AST, ALT, alkaline phosphatase, total bilirubin, BUN, serum creatinine, glucose, calcium, sodium, potassium, chloride, bicarbonate, total protein, albumin,

d: Coagulation profile: prothrombin time, activated partial-thromboplastin time, fibrinogen,

e: Performed in patients with complete clearance of blasts in the blood (+/- 7 Days)

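### Transplant outcomes are planned, but no follow-up item names transplant or its date, and follow-up ends once subsequent anti-cancer therapy begins

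*Combined protocol and SAP*

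**What the plan says.** **Outputs that need a transplant status or date.** The trial summary (1.1) lists "Percentage of patients bridging to transplantation" as a secondary objective, together with survival analyses censored at HSCT. Section 1.3.2 widens the first of these to the "percentage of patients bridging to allogeneic transplantation as well as time to transplantation", compared between arms. Section 1.4.2 adds, for both overall survival (OS) and leukemia-free survival (LFS): "Survival with censoring patients at the time of transplantation will also be evaluated". That section does not define bridging or time to transplantation, so neither has a denominator or a time origin.

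**Status at transplant.** Section 1.1 says "Patients eligible for HSCT will be taken off study prior to HSCT". Section 1.5.1 says "All transplant procedures occur off study". Neither says whether being off study ends follow-up or only protocol treatment.

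**What follow-up collects.** For phase II, section 1.18.2 lists: "Information regarding the first subsequent anti-cancer therapy (if applicable), documentation/date of last disease progression/relapse, and date of death". The follow-up row of the calendar (1.25.7) reads: "Subsequent anti-cancer therapy, documentation/date of last disease progression/relapse, date of death". Transplant appears in neither.

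**When follow-up ends.** Sections 1.1 and 1.18 set contact every 3 months for 24 months, ending earlier at death or at the start of subsequent anti-cancer therapy.

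**The concern.** Four planned outputs (bridging, time to transplantation, HSCT-censored OS and HSCT-censored LFS) depend on an event that takes place after the patient leaves the study. The plan does not name that event among the items to be collected. The stopping rule makes this worse, because contact ends when another therapy starts, and a transplant is most likely to follow at around that time.

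The loss would not fall evenly. Section 1.5.1 makes patients eligible for transplant once they are in remission with a donor, so the affected patients are mainly remitters. An arm with more remissions has more transplants to lose and more post-transplant survival time to cut off. Censored and uncensored survival are planned side by side to show how far transplant drives the result. That purpose fails if follow-up stops at transplant in both.

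**Working it through.** **1. Is there a data source under each reading of the text?** The documents do not say whether HSCT counts as subsequent anti-cancer therapy, or what being off study ends. The possible readings are:

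| Reading | Transplant recorded? | Relapse and death after transplant? |
|---|---|---|
| HSCT counts as subsequent therapy and comes first | Possibly, in the subsequent-therapy item; the list names a date for relapse and for death, but none explicitly for this therapy | Not required, because follow-up ends when it begins |
| HSCT does not count as subsequent therapy | No listed item records it | Yes, if follow-up continues |
| Another therapy comes first, then HSCT | Not sought, because contact has ended; the patient appears not bridged | Not required |
| Off study also ends follow-up | No | No |

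No reading secures both the transplant date and survival after transplant. In the first, uncensored OS and LFS are in effect censored at HSCT, so they add nothing to the HSCT-censored versions for these patients. In the second and fourth, the HSCT-censored analyses and time to transplantation lack their date.

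Section 1.15 does not close the gap. Transplant is not among its listed reasons for premature discontinuation, and it promises the same follow-up only where possible.

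**2. How many patients are involved?** The plan gives no figure for transplants, so the pool has to be derived.

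Inputs:
- response rates of 40% and 15%, and the stopping table from n = 8 to n = 24 in each arm (section 1.7);
- assumption: each response is known before the next patient is accrued;
- assumption, not in the documents: 30-60% of remitters proceed to transplant.

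Method: an exact binomial recursion on the number of responses. An arm stops when responses are at or below the futility number or at or above the efficacy number.

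Check against the plan's own figures: the recursion gives a probability of stopping for efficacy of 0.060 at 15% and 0.820 at 40%. These fit the stated limits of 10% type I error and 80% power, so the table has been read as intended.

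| | 40% arm | 15% arm |
|---|---|---|
| Expected patients, E[N] | 11.52 | 11.27 |
| Probability of reaching n = 24 | 0.063 | 0.062 |
| Expected cycle-1 remitters, p × E[N] | 0.40 × 11.52 = 4.6 | 0.15 × 11.27 = 1.7 |
| Transplants if 30% proceed | 0.30 × 4.61 = 1.4 | 0.30 × 1.69 = 0.5 |
| Transplants if 60% proceed | 0.60 × 4.61 = 2.8 | 0.60 × 1.69 = 1.0 |

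For example, if 2 versus 1 patients are transplanted and one transplant in the first arm goes unrecorded, the comparison becomes 1 versus 1.

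The calculation leaves out remissions in cycle 2, including those after placebo patients cross over. These would add transplants and blur the contrast between arms.

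**The case against.** **The subsequent-therapy item may capture the transplant.** Section 1.18.2 collects the first subsequent anti-cancer therapy. Section 1.5.1 allows up to two consolidation cycles on study and transplant as soon as there is remission and a donor. Going straight from study treatment to HSCT is therefore a route the plan provides for, and a site may well enter it there. How often off-study chemotherapy would come first is not stated. This stands as far as it goes: some transplants may be captured. But capture depends on an interpretation that the plan does not give, and under the stopping rule it costs the later relapse and survival data.

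**A reader might infer that no form collects transplant, or that bridging cannot be computed.** The documents do not support that. The case report forms are held in OnCore (section 1.20.1.1) and are not part of the documents. What can be shown is that the protocol text and calendar do not name the item, so the outcome is not assured.

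**A reader might infer that sections 1.1 and 1.5.1 contradict each other.** Both can be read as meaning off protocol treatment, and section 1.18 makes no transplant exception to the 24 months. This is an ambiguity, not a contradiction.

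**A reader might size the pool at 24 per arm, that is 24 × 0.40 = 9.6 versus 24 × 0.15 = 3.6 remitters.** The boundaries rule this out. An arm that continues past n = 23 has 5 to 7 responses, so at n = 24 it has 5 to 8. Only about 6% of trials take a given arm that far.

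**The impact is limited.** Section 1.7 says the trial is not powered for a formal comparison of the arms, and no stopping or success rule uses transplant. That is correct, and the primary endpoint is unaffected.

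**Conclusion.** The point holds for the secondary outcomes. As written, the plan gives bridging, time to transplantation and HSCT-censored OS and LFS no specified data source unless HSCT is captured as the first subsequent therapy. If it is so captured, the plan does not require the follow-up that uncensored OS and LFS need. This conclusion rests on the text alone and needs no numerical assumption.

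The size does rest on assumptions: the planning response rates, responses known before the next accrual, cycle-1 remissions only, and 30-60% of remitters proceeding. On these, about 1.4-2.8 versus 0.5-1.0 transplants are expected, few enough for one misclassified patient to matter. The change should be made, because it is cheap beforehand and the data are hard to recover once contact has ended.

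**What to change.** 1. In sections 1.1 and 1.5.1, state that leaving for HSCT ends protocol treatment, not follow-up.
2. In sections 1.1 and 1.18, amend the stopping rule so that follow-up for transplant, relapse and survival continues to 24 months after subsequent therapy or HSCT has begun, within the existing 24-month schedule.
3. Add HSCT (yes/no), its date and disease status at HSCT to the section 1.18 items and the calendar's follow-up column, for every patient whatever therapy came first.
4. In section 1.4.2, state the denominator for bridging and the time origin for time to transplantation. The origin could be randomisation for the phase II comparison, or treatment initiation to match the OS definition.

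Item 3 alone is not enough, because without item 2 there is no contact left at which to ask patients who have started another therapy.

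Cost: a few form fields, and further 3-monthly telephone calls within the existing 24 months for patients who start other therapy or go to transplant. No visit or procedure is added, and no treatment rule changes.
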